4.2.4.7. Intra-subject Dose Escalation

In Part 1, intra-subject dose escalations may be considered on a case-by-case basis, provided that the subject has completed at least the DLT observation period without

 \geq Grade 2 non disease-related toxicity in the first 21 days of therapy, that all subjects at the next highest dose level have completed the DLT observation period, and that prior approval has been obtained from the GSK Medical Monitor. Subjects may be dose-escalated to the highest cleared dose. Individual subjects may dose-escalate multiple times provided that the above criteria are met at each intra-subject dose escalation step. Safety assessments from these subjects will be included in the MTD determination.

Subjects approved for intra-subject dose escalation will initiate daily dosing from Day 1 of the higher dose (i.e., no dose interruption from Day 2 until Day 4) and will require additional PK sampling on Day 15 at the higher dose, as specified in Time and Events table (see Section 8.1). Additional safety assessments may be specified at the time of dose escalation or schedule modification based on the safety profile in previous subjects at the higher dose level. Intra-subject dose escalations or schedule modification will be discussed with investigators and approved by the GSK Medical Monitor and safety monitoring required will be specified in writing.

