4.3.2. R2PD Dose Selection

Subjects will start dosing on Day 1 with the dose and schedule selected as the RP2D in Part 1 of the study.

At a 21 March 2018 investigator meeting, 400 mg once daily (QD) was selected as the RP2D, based on safety, tolerability, efficacy, PK, and PD. Dose reductions and scheduled interruptions are permitted for toxicity and tolerability as described in Table 3. At that meeting, it was also determined that if emerging data demonstrated that 400 mg QD proved intolerable for a majority of subjects, that the starting dose for all subjects enrolled from that time forward may be reduced (e.g., to Dose level [DL]-1). The final dose selection will take into account all available clinical data, as well as a PK/PD model to predict the optimal dose with minimal cytopenias.

RP2D	400 mg QD
DL-1	300 mg QD
DL-2	200 mg QD
DL-3	200 mg QD, administered for 3 weeks, followed by a 1-week rest period

Table 3RP2D and Planned Dose Reduction

Note: These dose levels may be adjusted on a case-by-case basis after discussion with the GSK medical monitor.

Subsequent evaluation of safety and tolerability data was performed, using data from the 04 February 2019 data cut included in the IB for GSK3326595 [GlaxoSmithKline Document Number 2017N314773_03]. As of that date, 71 subjects had been treated at the 400 mg RP2D in the 204653 study. Of those 71 subjects, 33 (46%) required at least one dose reduction. Of the 33 subjects requiring dose reduction, the majority (23 subjects [70%]) remained on 300 mg for their duration on study. Overall, only 10 subjects (14% of the total number treated at 400 mg) required more than one dose reduction (i.e., to doses below 300 mg).

Clinical activity was observed in Part 1, in subjects with ACC who were treated at doses of 300 mg and below. Of the three patients who exhibited confirmed partial responses, two were started at a dose of 200 mg QD and remained at that dose throughout their time on study. The third responder began treatment with GSK3326595 at 400 mg QD, but dose reduced to 300 mg QD after the first month on treatment.

All new subjects enrolled, following approval of Protocol Amendment 4 (food effect and relative bioavailability sub-study in Part 1, and all dose expansion cohorts in Part 2), will start on 300 mg QD (i.e., at Dose level-1 [DL-1] in Table 3). In all cohorts, dose reduction for toxicity will be permitted, as described in Table 3.

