5.1.1. Treatment Display

The actual treatment of a subject will be derived from exposure data. The first dose the subject received will be used as actual treatment. Scheduled (planned) treatment is collected on dosing regimen eCRF page. Efficacy, safety and PK analysis will be based on the All Treated Population.

Per Protocol Amendment 7, if the GSK3326595 tablet bioavailability is comparable to that of the GSK3326595 capsules from Part 1 Food Effect and Relative Bioavailability Sub-study, all new and ongoing subjects may be switched from capsules to tablets for the remainder of the study, once they have been notified by the Sponsor. As of 3 Nov 2021, per GSK communication, tablet and capsule cohorts within the same disease/dosage groups will be combined.

The leading dose formulation (tablet or capsule) and the leading dose level are specified in treatment.

- For Part 1 dose escalation cohorts, all data will be pooled and descriptive analyses summarized and listed by investigated GSK3326595 dose under QD dose escalation cohort or BID dose escalation cohort. PK/PD expansion cohorts will be summarized together with dose escalation cohorts dose level. If applicable, Part 1 Food Effect Relative Bioavailability Sub-study data will also be included in Part 1 summary tables as a separate column. The treatment groups for Part 1 are:
 - Part 1 QD Dose GSK3326595 12.5 mg Capsule
 - Part 1 QD Dose GSK3326595 25 mg Capsule
 - Part 1 QD Dose GSK3326595 50 mg Capsule
 - Part 1 QD Dose GSK3326595 100 mg Capsule
 - Part 1 QD Dose GSK3326595 200 mg Capsule
 - Part 1 QD Dose GSK3326595 300 mg Capsule
 - Part 1 QD Dose GSK3326595 400 mg Capsule
 - Part 1 QD Dose GSK3326595 600 mg Capsule
 - Part 1 BID Dose GSK3326595 50 mg Capsule
 - Part 1 BID Dose GSK3326595 100 mg Capsule
 - Part 1 BID Dose GSK3326595 150 mg Capsule
 - Part 1 BID Dose GSK3326595 200 mg Capsule
 - Food Effect and Relative Bioavailability Sub-study 300mg QD (apply to table/figures)
 - Part 1 Food Effect 300mg Sequence 1 (Tablet Fasted Tablet Fed Capsule Fasted) (apply to listings)
 - Part 1 Food Effect 300mg Sequence 2 (Tablet Fed Tablet Fasted Capsule Fasted) (apply to listings)
- For Part 2 dose expansion cohorts, data will be summarized and listed by cohorts. The treatment groups for Part 2 are:
 - Part 2 TNBC 400mg QD Capsule Cohort

- Part 2 mTCC 400mg QD Capsule Cohort
- Part 2 GBM 400mg QD Capsule Cohort
- Part 2 ER+BC 400mg QD Capsule Cohort
- Part 2 HPV+ 400mg QD Capsule Cohort

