15.5.2. Reporting Standards

General						
• The current GSK Integrated Data Standards Library (IDSL) will be applied for reporting,						
unless otherwise stated:						
4.03 to 4.23: General Principles						
 5.01 to 5.08: Principles Related to Data Listings 						
 6.01 to 6.11: Principles Related to Summary Tables 						
 7.01 to 7.13: Principles Related to Graphics 						
Formats						
All data will be reported according with the All Treated Population, according to the						
actual treatment the subject received unless otherwise stated.						
 GSK IDSL Statistical Principles (5.03 & 6.06.3) for decimal places (DP's) will be adopted 						
for reporting of data based on the raw data collected.						
 Numeric data will be reported at the precision collected on the eCRF. 						
The reported precision from non eCRF sources will follow the IDSL statistical principles.						
Planned and Actual Time						
 Reporting for tables, figures and formal statistical analyses : 						
 Planned time relative to dosing will be used in figures, summaries, statistical 						
analyses and calculation of any derived parameters, unless otherwise stated.						
 The impact of any major deviation from the planned assessment times and/or 						
scheduled visit days on the analyses and interpretation of the results will be						
assessed as appropriate.						
Reporting for data listings:						
Planned and actual time relative to study drug dosing will be shown in listings						
(Refer to IDSL Statistical Principle 5.05.1).						
Unscheduled Visits						
Unscheduled visits will not be included in summary tables except for most extreme						
result reporting (e.g. worst grade post-baseline), as well as tumor assessments.						

	Unscheduled visits will not be included in figures except for tumor assessments.						
	All unschedu	All unscheduled visits will be included in listings.					
De	Descriptive Summary Statistics						
1.	Continuous Data	1. Refer to IDSL Statistical Principle 6.06.1					
1.	Categorical Data	2. N. n. frequency. %					

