15.6.2. Study Population

Demographics

Age
GSK standard IDSL algorithms will be used for calculating age where birth date will be
imputed as follows:
 Any subject with a missing day will have this imputed as day '15'.
 Any subject with a missing date and month will have this imputed as '30th June'.
 Birth date will be presented in listings as 'YYYY'.
Body Mass Index (BMI)
 Calculated as Weight (kg) / [Height (m)²
Extent of Exposure
GSK3326595
 Number of days of exposure (duration on study treatment) to study drug will be
calculated based on the formula:
Duration of Exposure in Days = Treatment Stop Date – Treatment Start Date + 1
 Participants who were randomized but did not report a treatment start date will be
categorised as having zero days of exposure.
 The cumulative dose will be based on the formula:
Cumulative Dose = Sum of (Number of Days x Total Daily Dose)
If there are any treatment breaks during the study, exposure data will be adjusted accordingly.
Pembrolizumab
 Extent of exposure will be calculated based on treatment cycles derived based
on cycle start dates in the exposure dataset
 Duration on study treatment will be calculated based on the formula:

Duration on study treatment = Last Treatment Stop Date – First Treatment Start Date + [lag time, e.g., Duration of Cycle]

Take into account of death date if a lag time>1, e.g., Duration of Cycle is used.

- Participants who were randomized but did not report a treatment start date will be categorised as having zero days of exposure.
- Combination Treatments (Part 3)
- Extent of exposure will be calculated for each treatment component
- Duration of treatment will be calculated based on the formula:

Duration on study treatment = Maximum of ([IV Treatment Stop Date + lag time], [Oral Treatment Stop Date]) – (Minimum of Treatment Start Date) + 1

Take into account of death date if a lag time>1, e.g., Duration of Cycle is used.

• Participants who were randomized but did not report a treatment start date will be categorized as having zero days of exposure

Actual Treatment

• Subject's actual treatment will be derived from [exposure data] [study treatment data provided by Clinical Operations]. If a subject's actual treatment is the same as assigned treatment, actual treatment is the assigned treatment; if a subject received treatment different from assigned treatment for the entire duration of treatment, actual treatment is different from assigned treatment.

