15.12.9. Pharmacokinetic Tables

		IDSL / Example			
No.	Population	Shell	Title	Programming Notes	Deliverable
4.1	РК	PK01	Summary of GSK3326595 Pharmacokinetic Concentration- Time Data by Treatment and Study Day	Use descriptive statistics (n, mean, SD, median, min and max) by planned relative assessment time; concentrations in ng/mL. All planned time points. by dose for Part 1, by cohort for parts 2 and 3 also by 300mg, 400mg QD across all parts, For Part 3, include Pembrolizumab	SAC
4.2	PK	GSK- provided	Summary of Pembrolizumab Immunogenicity Data by Treatment and Study Day	Part 3 only	SAC
4.3	РК	PK06	Summary of Derived GSK3326595 Pharmacokinetic Parameters by Treatment and Study Day	PK parameters: Cmax, Tmax, Ctrough, AUC0-t, tlast, AUC0-tau, AUCinf, t½, λz , TI and AR determined from the concentration-time data in ng/ml; descriptive summaries: mean, SD, median, min, max, geometric mean & SD, CV%, and 95%CI of log-transformed	SAC

No.	Population	IDSL / Example Shell	Title	Programming Notes	Deliverable
				parameters, if applicable. by dose for Part 1, by cohort for parts 2 and 3 also by 300mg, 400mg QD across all parts	
4.5	PK	custom	Dose Proportionality Comparison (Power Model) for AUC(0-inf:=) and Cmax of GSK3326595	Provide separately for QD regimens and BID regimens of Part 1 only	SAC
4.6	PK	NA	Food Effect Sub-Study	<previously done=""></previously>	IA
4.7	PK	NA	Relative Bio-Availability Sub-Study	<previously done=""></previously>	IA

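### PK taken after a dose change falls under the starting dose, because the SAP labels each subject by the first dose received

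*SAP*

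**What the plan says.** - SAP 5.1.1 (Treatment Display) sets one label per subject: "The first dose the subject received will be used as actual treatment". The same paragraph brings PK in: "Efficacy, safety and PK analysis will be based on the All Treated Population".
- SAP 15.5.2 (Reporting Standards) reports all data by the "actual treatment the subject received unless otherwise stated".
- SAP 15.6.2 gives a second definition, also at subject level: "if a subject received treatment different from assigned treatment for the entire duration of treatment, actual treatment is different from assigned treatment".
- SAP 15.12.9 sets the layout of Table 4.1 (concentrations): "All planned time points. by dose for Part 1, by cohort for parts 2 and 3 also by 300mg, 400mg QD across all parts". Table 4.3 (derived parameters) uses the same grouping. Both are titled by treatment and study day.
- SAP 9.2.1 defines TI and AR as a Day 15 AUC over a Day 1 AUC and sets no condition on dose.
- Protocol 11.10.2.2.2 has Cmax and AUC, including steady-state AUC, plotted against the dose administered.
- The protocol expects doses to change. Section 4.3.2 on the 400 mg starting dose: "Of those 71 subjects, 33 (46%) required at least one dose reduction". Section 4.2.4.7 on Part 1: "Individual subjects may dose-escalate multiple times provided that the above criteria are met at each intra-subject dose escalation step". That section also requires a further Day 15 PK draw at the higher dose.

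**The concern.** A label fixed at the first dose is correct on Day 1 and stays correct only while the dose does not change. PK sampling continues after that: pre-dose samples are taken at later scheduled visits in all three parts (footnotes to protocol Tables 9, 14 and 15). If a subject who started at 400 mg is taking 300 mg at a later sample, the stated rule still files the result under 400 mg.

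What is at stake is the reported description of exposure by dose, a Part 1 secondary objective and a secondary analysis under SAP 2.1. Reductions lower the apparent later exposure at 400 mg and narrow its contrast with 300 mg. Escalations raise apparent exposure at low starting doses. A Day 15 to Day 1 ratio computed across a dose change reads as a change in kinetics when it is a change in dose.

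**Working it through.** **1. Which records the rule mislabels**

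| PK record | Label under SAP 5.1.1 | Effect |
|---|---|---|
| Day 1 profile | First dose | Correct |
| Food-effect and bioavailability periods (SAP 9.2.2.2) | Treatment in that period; wrong dose or formulation excluded | Not affected |
| Scheduled Day 15 profile, dose unchanged | First dose | Correct |
| Day 15 profile rescheduled under protocol 8.2.2, dose since reduced | First dose | Mislabelled |
| Extra Day 15 profile after escalation (protocol 4.2.4.7) | First dose | Mislabelled if it enters the summary |
| Later pre-dose samples after any dose change | First dose | Mislabelled |

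Protocol 8.2.2 moves the Day 15 draw when the subject is off drug or not at steady state. It requires steady state but not an unchanged dose, and Appendix 2 (Table 24) allows dosing to resume at the same or a lower dose. Escalation is open only after the 21-day DLT period, so it cannot touch a Day 15 profile drawn on schedule.

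The SAP does not say how the extra post-escalation profile is handled. SAP 5.1 keeps unscheduled visits out of ordinary summaries. SAP 15.6.1 analyses the latest result when one scheduled assessment has several on different days. Depending on how the profile is coded, it is dropped or it replaces the starting-dose profile under the starting-dose label.

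**2. The plan's own figures (protocol 4.3.2)**

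- At least one reduction: 33/71 = 46.5% (stated 46%).
- Of those, stayed at 300 mg: 23/33 = 69.7% (stated 70%).
- Reduced below 300 mg: 10/71 = 14.1% (stated 14%), and 33 − 23 = 10.
- Not reduced: 71 − 33 = 38.

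**3. Mean dose behind the 400 mg label**

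Assumptions: exposure proportional to dose, and the 10 subjects below 300 mg taken as being at 200 mg. If every reduction came before the sample:

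(38×400 + 23×300 + 10×200)/71 = 24,100/71 = 339.4 mg, or 339.4/400 − 1 = −15.1%.

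If only a fraction f of reductions came before the sample, the mean is 400 − f×(400 − 339.4):

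| f | Mean dose (mg) | Difference from 400 mg |
|---|---|---|
| 0 | 400.0 | 0% |
| 0.10 | 393.9 | −1.5% (about −2%) |
| 0.25 | 384.9 | −3.8% |
| 0.50 | 369.7 | −7.6% (about −8%) |
| 1 | 339.4 | −15.1% |

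The documents do not give f for any sampling day.

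**4. TI and AR**

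With linear PK, a Day 15 AUC at 300 mg is 300/400 = 0.75 of its value at 400 mg. The Day 1 denominator stays at 400 mg, so TI and AR are both multiplied by 0.75 and read 25% low for that subject.

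**The case against.** The case on the other side has five parts.

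*Scope.* A reader might infer that every PK concentration and parameter is mislabelled. That is wrong: Day 1 data and the sub-study are correct. The dose-proportionality model uses AUC(0-∞), which the protocol ties to single dose, and Cmax, for which the SAP gives no day. Parts 2 and 3 are grouped mainly by cohort, and protocol 11.10.2.2.2 itself asks for descriptive summaries by dose cohort. A cohort summary is legitimate if read as one. The pooled 300/400 mg summaries across parts are not cohort summaries, so the point stands there and in the Part 1 by-dose columns.

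*Safeguards.* A reader might infer that PK data can be excluded only for protocol deviations (the note in SAP 4.1). SAP 5.1.2 also lets Clinical Pharmacology drop data points after the non-compartmental analysis. That is discretionary, has no stated criterion and is not tied to a dose change.

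*Reach of TI and AR.* Day 15 sampling in Parts 2 and 3 is sparse, so these ratios are realistically derivable only from the Part 1 serial profiles. The 71 subjects are study-wide and are not the TI/AR population. This stands.

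*Size.* The −15% needs all 33 reductions to precede the sample. The one dated example in protocol 4.3.2 reduced after the first month, which is after Day 15. A reader might also point to a subject escalated from 12.5 to 200 mg, whose later results would be about 16 times too high for the 12.5 mg column (200/12.5). The documents report no such subject and no frequency, so that is arithmetic on a hypothetical case.

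*Consequence.* A reader might infer that mislabelled tables influenced the RP2D or the later move to 300 mg. The RP2D was chosen in March 2018, the move came with Amendment 4 in 2019, and version 1.0 of the SAP is dated September 2022. These tables cannot have informed either decision.

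These points limit the reach and size of the effect. None supplies a rule for PK taken after a dose change.

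**Conclusion.** The concern holds for PK records taken after a dose change. As written, SAP 5.1.1 and 15.5.2 place them by default under the starting dose in Tables 4.1 and 4.3. This is a stated rule that gives the wrong dose label, not merely missing detail, and it departs from the protocol's plan to relate exposure to the dose administered.

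The effect on the mean dose behind the 400 mg label lies between 0% and −15%, under dose-proportional exposure and with sub-300 mg doses taken as 200 mg. The position within that range depends on reduction timing that the documents do not give. TI and AR are 25% low for a Part 1 subject reduced from 400 to 300 mg before the Day 15 profile, under linear PK. The effect of escalations cannot be sized. The point concerns the reported PK by dose. It does not bear on the efficacy or safety analyses, or on dose decisions already made. It should be corrected.

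**What to change.** - In SAP 5.1.1, add a PK exception. For PK summaries by dose (Tables 4.1 and 4.3, and Figures 4.1–4.3 where they show post-Day 1 data), classify each post-Day 1 record by the GSK3326595 dose and regimen in effect at sampling, taken from exposure data. Alternatively, exclude records taken after a dose change from those summaries and flag them. Show the dose at sampling in Listings 79 and 82.
- In SAP 9.2.1, derive TI and AR only when the Day 1 and Day 15 doses are equal, or dose-normalise both AUCs.
- Flag samples drawn during an interruption and leave them out of the summaries.
- State how the extra Day 15 profile after escalation is coded, so that the latest-result rule in SAP 15.6.1 does not let it replace the starting-dose profile.
- Reconcile the definitions of actual treatment in SAP 5.1.1 and 15.6.2.

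Tablet and capsule can stay combined, as the SAP has already decided. The cost is SAP wording and a merge of PK with exposure records already collected. The downside is some smaller cells.
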